14.7. Criteria for Early Stopping Due to Unacceptable Rates of Adverse Events

Criteria will be in place for halting enrollment and treatment due to safety findings:

- Any fatality that is at least possibly related to treatment calls for immediately stopping accrual and treatment. If attribution is in doubt, the study should be halted until attribution is definitively determined and a decision is made by the study team.
- Two or more observations of a secondary myelodysplastic syndrome or AML or secondary malignancy attributed to tazemetostat will result in stopping accrual and treatment. (Note: observations may not occur during the study period and may occur later, after it is too late to stop accrual.)
- Continuous monitoring with Pocock-like boundaries using the method of Ivanova (Ivanova, 2005) will be utilized for other categories of adverse events, with following rates applied to the continuous stopping rules:
- Combined rate of reportable SAE or SUSAR: 10%
 - Any single category of grade > 3 AE: 50%
 - Grade >3 non-hematologic AE overall: 30%

A table of stopping boundaries for these criteria are provided in Appendix 5. These criteria are independent of the futility analysis for efficacy and will be applied to all subjects that receive any treatment with tazemetostat, regardless of mutation status. See Appendix 2 for details. The stopping rules assume a full accrual of 54 subjects in order to retain statistical properties.

However, if the study stops early due to futility, any bias introduced in the stopping rules due to a change in total accrual should no longer be a concern.

15. DIRECT ACCESS TO SOURCE DATA/DOCUMENTS

15.1. Study Monitoring

Before an investigational site can enter a subject into the study, a representative of Epizyme will visit the investigational study site or conduct a remote visit, if necessary, to:

- Determine the adequacy of the facilities
- Discuss with the Investigator(s) and other personnel their responsibilities with regard to protocol adherence, and the responsibilities of Epizyme or its representatives. This will be documented in a Clinical Study Agreement between Epizyme and the Investigator.

During the study, a monitor from Epizyme or representative will have regular contact with the investigational site, for the following:

- Provide information and support to the Investigator, Sub-Investigator(s) and study staff
- Confirm that facilities remain acceptable
- Confirm that the investigational team is adhering to the protocol, that data are being accurately recorded in the case report forms, and that investigational product accountability checks are being performed
- Perform source data verification. This includes a comparison of the data in the case report forms with the subject's medical records at the hospital or practice, and other records relevant to the study. This will require direct access to all original records for each subject (eg, clinic charts).
- Record and report any protocol deviations not previously sent to Epizyme.
- Confirm AEs and SAEs have been properly documented on CRFs and confirm any SAEs have been forwarded to Epizyme and those SAEs that met criteria for reporting have been forwarded to the IRB.

The monitor will be available between visits if the Investigator(s) or other staff needs information or advice.

15.2. Audits and Inspections

Authorized representatives of Epizyme, a regulatory authority, an Independent Ethics Committee or an Institutional Review Board may visit the site to perform audits or inspections, including source data verification. The purpose of an Epizyme audit or inspection is to systematically and independently examine all study-related activities and documents to determine whether these activities were conducted, and data were recorded, analyzed, and accurately reported according to the protocol, Good Clinical Practice guidelines of the International Conference on Harmonization, and any applicable regulatory requirements. The Investigator should contact Epizyme immediately if contacted by a regulatory agency about an inspection.

15.3. Institutional Review Board (IRB)

The Principal Investigator must obtain IRB/IEC approval for the investigation. Initial IRB/IEC approval, and all materials approved by the IRB/IEC for this study including the subject consent form and recruitment materials must be maintained by the Investigator and made available for inspection.

16. DATA QUALITY ASSURANCE

To ensure compliance with Good Clinical Practices and all applicable regulatory requirements, Epizyme may conduct a quality assurance audit. Please see Section 15.2 for more details regarding the audit process.

17. ETHICS

17.1. Ethics Review

The final study protocol, including the final version of the Informed Consent Form, must be approved or given a favorable opinion in writing by an IRB or IEC as appropriate. The Investigator must submit written approval to Epizyme before he or she can enroll any subject into the study.

The Principal Investigator is responsible for informing the IRB or IEC of any amendment to the protocol in accordance with local requirements. In addition, the IRB or IEC must approve all advertising used to recruit subjects for the study. The protocol must be re-approved by the IRB or IEC upon receipt of amendments and annually, as local regulations require.

The Principal Investigator is also responsible for providing the IRB with reports of any reportable serious adverse drug reactions from any other study conducted with the investigational product. Epizyme will provide this information to the Principal Investigator.

Progress reports and notifications of serious adverse drug reactions will be provided to the IRB or IEC according to local regulations and guidelines.

17.2. Ethical Conduct of the Study

The procedures set out in this study protocol, pertaining to the conduct, evaluation, and documentation of this study, are designed to ensure that the Sponsor and Investigators abide by GCP as described in the current ICH Tripartite Guideline E6: GCP: Consolidated Guideline. Compliance with these regulations also constitutes compliance with the ethical principles described in the current revision of the Declaration of Helsinki. The study will also be carried out in keeping with all applicable country and local legal and regulatory requirements.

17.3. Written Informed Consent

The Principal Investigator(s) at each center will ensure that the subject is given full and adequate oral and written information about the nature, purpose, possible risk and benefit of the study. Subjects must also be notified that they are free to discontinue from the study at any time. The subject should be given the opportunity to ask questions and allowed time to consider the information provided.

The subject's signed and dated informed consent must be obtained before conducting any study procedures.

The Principal Investigator(s) must maintain the original, signed Informed Consent Form. A copy of the signed Informed Consent Form must be given to the subject.

18. DATA HANDLING AND RECORD KEEPING

18.1. Inspection of Records

Epizyme will be allowed to conduct site visits to the investigation facilities for the purpose of monitoring any aspect of the study. The Investigator agrees to allow the monitor to inspect the drug storage area, study drug stocks, drug accountability records, subject charts and study source documents, and other records relative to study conduct.

18.2. Retention of Records

The Principal Investigator must maintain all documentation relating to the study for a period of 2 years after the last marketing application approval, or if not approved 2 years following the discontinuance of the test article for investigation. If it becomes necessary for Epizyme or the Regulatory Authority to review any documentation relating to the study, the Investigator must permit access to such records.

18.3. Data Management

Data required by the protocol will be collected on a CRF and entered into an Electronic Data Capture clinical database that is compliant with all regulatory requirements.

The Investigator has ultimate responsibility for the collection and reporting of all clinical, safety, and laboratory data entered on the CRF. The Investigator or designee as identified on Form FDA 1572 must sign the CRF casebook to attest to its accuracy, authenticity, and completeness.

The completed eCRFs are the sole property of the Sponsor and must not be made available in any form to third parties, except for authorized representatives of the Sponsor or appropriate regulatory authorities, without written permission from the Sponsor.

18.4. Recording of Data

A CRF is required for each subject and must be completed by qualified and authorized personnel. Only data required by the protocol for the purposes of the study should be reported on the CRF. All data on the CRF must reflect the corresponding source document. Any corrections to entries made on the CRF must be documented in a valid audit trail.

18.5. Identification of Source Data

The following items in the CRF will be handled as source data:

- Study drug compliance (eg, the reason for dose increase/reduction)
- Discontinuation information
- Sampling date and time for the drug concentration
- Sampling date and time for the clinical laboratory test
- Comments and other information on AEs (eg, severity, relationship to study drug, outcome)

18.6. Handling of Study Drug

All tazemetostat will be supplied to the PI (or a designated pharmacist) by Epizyme. Drug supplies must be kept in an appropriate secure area (eg, locked cabinet) and stored according to the conditions specified on the drug label. The Investigator (or a designated pharmacist) must maintain an accurate record of the shipment and dispensing of the study drug in a drug accountability ledger, a copy of which must be given to the Sponsor at the end of the study. An accurate record of the date and amount of study drug dispensed to each subject must be available for inspection at any time. Once study drug has been received by the investigational site, the assigned review personnel may request the records for reviewing these documents along with all other study conduct documents at appropriate intervals during investigational site visits.

All drug supplies are to be used only for this protocol and not for any other purpose. The Investigator (or a designated pharmacist) must not destroy any drug labels or any partly used or unused drug supply before approval to do so by Epizyme. At the conclusion of the study and as appropriate during the course of the study, the Investigator (or a designated pharmacist) will either return all used and unused drug containers, drug labels, and a copy of the completed drug disposition form to the Epizyme designated contractor or, where approval is given by Epizyme, will destroy supplies and containers at the investigational site.

18.7. Disclosure and Confidentiality

The contents of this protocol and any amendments and results obtained during the course of this study will be kept confidential by the Investigator, the Investigator's staff, and the IRB/IEC and will not be disclosed in whole or in part to others or used for any purpose other than reviewing or performing the study without the written consent of the coordinating center. No data collected as part of this study will be utilized in any written work, including publications, without the written consent of the coordinating center. These obligations of confidentiality and non-use shall in no way diminish such obligations as set forth in the Confidentiality Agreement between the Sponsor and the Investigator.

All persons assisting in the performance of this study must be bound by the obligations of confidentiality and non-use set forth in the Confidentiality Agreement between the Investigator and the coordinating center.

19. PUBLICATION POLICY

A summary of the study results will be made publicly available within 12 months of reaching the end of the study, defined as the date of the last subject last visit. Clinical study results will be made publicly available in compliance with local legislation and guidelines.

If a manuscript is published in a peer-reviewed journal, then that initial release may be an abstract that meets the requirements of the International Committee of Medical Journal Editors. All manuscripts, abstracts or other modes of presentation arising from the results of the study must be reviewed and approved in writing by the Sponsor, in advance of submission. The review is aimed at protecting the Sponsor's proprietary information existing either at the date of the commencement of the study or generated during the study.

The detailed obligations regarding the publication of any data, material results, or other information, generated or created in relation to the study shall be set out in the agreement between each Investigator and the Sponsor.

1. LIST OF ABBREVIATIONS

Table 1: List of Abbreviations

Abbreviation	Term
AE	Adverse Event
BMI	Body mass index
CRF	Case Report Form
CSR	Clinical Study Report
ECG	Electrocardiogram
IP	Investigational Product
MedDRA	Medical Dictionary for Regulatory Activities Terminology
SAE	Serious Adverse Event
TEAE	Treatment Emergent Adverse Event

2. INTRODUCTION

This statistical analysis plan (SAP) describes the data presentation to be used for analyzing and reporting efficacy and safety data for study EZH-1401. This document has been prepared based on EZH-1401 study protocol amendment #2 (dated 12OCT2021). This SAP is to be interpreted in conjunction with the protocol, and supersedes the statistical considerations described in the protocol.

The study was terminated early and a synoptic clinical study report (CSR) will be prepared based on the final analysis after data base lock. If there were any deviations to the planned statistical analyses from this SAP, the justification for any such differences will be fully documented in the synoptic CSR.

3. OVERALL STUDY DESIGN

3.1. Treatment of Study Drugs

Tazemetostat 800 mg twice daily (BID) will be administered starting on Cycle 1 Day 1 (C1D1, 28 days per cycle). Tazemetostat is supplied by Epizyme in pre-counted, appropriately labeled bottles. Tazemetostat will be administered from C1D1 to the end of Cycle 24, for a total of 24 months of therapy.

Rituximab will be administered by either subcutaneous injection or IV infusion according to the regional product prescribing information and labeling. Rituximab will be administered at a dose of 375 mg/m² on Days 1, 8, 15, and 22 of Cycle 1, and then on Day 1 of Cycles 3 through 6, accounting for an additional 4 doses, ie, a total of 8 doses of rituximab in 6 cycles. Rituximab will be procured by the clinical sites from commercial sources.

3.2. Sample Size Considerations

3.2.1. Sample Size Justifications

The primary objective of this study is to evaluate the overall response rate obtained in subjects with R/R FL and wild-type (WT) EZH2 status, treated with the combination of rituximab and tazemetostat. Given the historical data with single agent rituximab ([McLaughlin, 1998](#) [Leonard, 2019](#)) we would consider the combined regimen to be of no further interest if the ORR were 50% or less, but of considerable interest if the ORR were at least 70%.

Simon's two-stage design (Simon, 1989) will be used. The null hypothesis that the true response rate is 50% will be tested against the one-sided alternative. In the first stage, 15 subjects will be accrued. If there are 8 or fewer responses in these 15 subjects, the regimen will be considered as futile.

Subject enrollment will continue during futility analysis. If 9 responses or greater (CR + PR) are seen in the initial 15 subjects, additional subjects will be accrued for a total of 54 evaluable subjects. The Sponsor expects 80% of enrolled subjects to have WT EZH2 status. Consequently, the study will enroll approximately 43 WT subjects as well as approximately 11 MT subjects. With an estimated early dropout rate of 10%, this study estimates a total accrual of 59 subjects. For the primary analysis, the null hypothesis will be rejected if 27 or more responses (CR + PR) are observed in the first 43 evaluable subjects regardless of mutation status. This design yields a one-sided type I error rate of 0.05 and power of 0.801 when the true response rate is 70%. If the primary analysis is successful, full analysis will be conducted once 54 evaluable subjects are available regardless of mutation status. Subjects in the FAS will be stratified to 2 subgroups depending on their EZH2 mutation status (WT vs MT). The sample size calculation is showing in [Appendix 1](#).

Assuming accrual takes place over 24 months, with at least an additional 12 months of follow-up for progression, there would be approximately 65% power to rule out a benchmark median PFS of 12 months against the alternative of a true PFS of 18 months (one-sided, 0.05 level test) in the primary analysis subset of 43 subjects with at least 26 PFS events. If PFS is similar in both subsets regardless of EZH2 status, then there would be 80% power for the same analysis in the combined FAS of 54 subjects with at least 33 PFS events.

The reporting of response rate in the MT EZH2 subset (anticipated to be 11 subjects) will have very little precision and is exploratory only. Note, the subjects with MT EZH2 status will be included in all primary safety analyses.

3.2.2. Sample Size Re-estimation

Not applicable.

3.3. Randomization

This is an open-label, one-arm study. There is no randomization in this study.

[figure not shown]
3.4. Clinical Assessments

Tumor assessments

Tumor assessments will be performed based upon Lugano 2014 criteria at each assessment time point. Investigator determined response results at each assessment time point will be entered into the appropriate CRF.

Biomarker Assessments

CCI

ECOG Performance Status

An ECOG performance status should be done at each visit as designated in the Schedule of Visits and Procedures (Table 2).

Survival Follow-up Assessments

All subjects who complete the planned 24-month tazemetostat treatment portion of the study will be followed for survival follow-up. Survival follow-up will be done every 6 months for 2 years, or until the patient has disease progression or death, whichever comes first. Survival follow up will be done via chart review of routine clinic appointments, patient phone calls to assess alive/deceased status and disease progression status.

4. STUDY OBJECTIVE(S) AND ENDPOINT(S)

4.1. Study Objective(s)

Primary Objectives:

- To assess the objective response rate (ORR; complete response + partial response [CR + PR]) of tazemetostat in combination with rituximab in subjects with relapsed/refractory (R/R) FL and without EZH2 mutation status

Secondary Objectives:

- To evaluate safety of the combination of tazemetostat and rituximab by assessing incidence of AEs, change of vital signs, lab results, and physical exam findings from baseline
- To estimate the median progression-free survival (PFS) of tazemetostat in combination with rituximab at 2 years in R/R follicular lymphoma with wild type mutation status, and in the pooled group regardless of mutation status
- To explore response to treatment in the subset of subjects with EZH2 mutant status
- Evaluation of efficacy outcomes in rituximab refractory subjects

4.2. Study Endpoint(s)

Primary Endpoint:

- ORR, defined as the proportion of subjects achieving PR or CR according to the 2014 Lugano Classification as assessed by Investigator and independent review committee (IRC) at the following timepoints: Cycle 3, Cycle 6, Cycle 12, Cycle 18, and Cycle 24

Secondary Endpoints:

- Type, frequency, severity, timing of onset, duration, and relationship to study drug of any treatment-emergent AEs or abnormalities of laboratory tests; serious adverse events (SAEs); dose-limiting toxicities (DLTs), or AEs leading to discontinuation of study treatment or death
- PFS, assessed by a blinded IRC
- Duration of response (DOR), defined as the time from the earliest date of CR or PR per the 2014
- Lugano Classification to documented progression or death, whichever comes first, as assessed by IRC.
- ORR in the pooled group regardless of mutation status and in a subset of subjects with MT EZH2 at the following time points: Cycle 3, Cycle 6, Cycle 12, Cycle 18, and Cycle 24 for tazemetostat in combination with rituximab using 2014 Lugano Classification.

- ORR in rituximab refractory subjects at the following time points: Cycle 3, Cycle 6, Cycle 12, Cycle 18, and Cycle 24 for tazemetostat in combination with rituximab using 2014 Lugano Classification

Exploratory Endpoints:

- OS, defined as the interval of time between the date of the first dose of study drug and the date of death due to any cause.

4.3. Statistical Hypotheses

A one-sample Chi-square test with a 0.025 1-sided significance level to test the null hypothesis that overall response rate (ORR) will be $\leq 50\%$ versus the alternative hypothesis that ORR will be $> 70\%$.

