14.2. Primary Efficacy Analyses

ORR is defined as the proportion of subjects achieving a CR or PR according to the 2014 Lugano Classification (Appendix 3) as assessed by Investigator and blinded IRC at the following time points: Cycle 3, Cycle 6, Cycle 12, Cycle 18, and Cycle 24.

Subjects with a best response of unknown/non-evaluable response will be treated as non-responders, (i.e., they will be included in the denominator only when calculating the percentage). ORR will be presented with corresponding 2-sided 95% confidence intervals (CIs). This analysis will be performed on a subset of the FAS that includes all subjects with WT EZH2 status.

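### Does the one-sided 0.025 chi-square test in SAP 4.3, set against the Simon rule at one-sided 0.05 in SAP 3.2.1, require a change to the plan?

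*SAP*

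**What the plan says.** SAP 3.2.1 gives the design in full. The null rate is 50%: "The null hypothesis that the true response rate is 50% will be tested against the one-sided alternative". The regimen is "of considerable interest if the ORR were at least 70" per cent. The first-stage rule is "If there are 8 or fewer responses in these 15 subjects, the regimen will be considered as futile". The final rule rejects at 27 or more responses among the first 43 evaluable subjects, whatever their EZH2 status. The stated properties are: "This design yields a one-sided type I error rate of 0.05 and power of 0.801 when the true response rate is 70" per cent. Protocol 14.6 and the synopsis give the same null, stage rule, cut-off, error rate and power.

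SAP 4.3 differs. It names "A one-sample Chi-square test with a 0.025 1-sided significance level to test the null hypothesis" that ORR is at most 50%, "versus the alternative hypothesis that ORR will be" above 70%. It mentions no stages, no sample size and no response count.

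On precedence, the SAP says that it "supersedes the statistical considerations described in the protocol", and Protocol 14 says that the SAP governs where the two differ.

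On what will be done, SAP 5.2 records early termination with 5 treated patients and drops the analyses planned in the protocol. SAP 5.1 lists no interim analysis. SAP 8 excludes futility and efficacy analyses, and SAP 9 repeats the exclusion for efficacy. SAP 6 defines only an enrolled population and a safety population.

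**The concern.** One document states two primary tests that differ in method, significance level and rejection rule. A trial with exactly 27 responses in 43 would succeed under SAP 3.2.1 and could fail under SAP 4.3. The precedence clauses do not help, because they rank the SAP above the protocol and this conflict lies inside the SAP.

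The hypotheses in SAP 4.3 are also badly formed. A true ORR above 50% and up to 70% belongs to neither the null nor the alternative. The 70% is the rate at which power is computed, and SAP 4.3 has turned it into the boundary of the alternative.

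In a trial running to completion this would matter: the success criterion for the primary endpoint would be open to choice after the data were seen.

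**Working it through.** **Inputs.** From SAP 3.2.1: null rate 0.50, target rate 0.70, first stage 15 subjects with continuation at 9 or more responses, total 43, rejection at 27 or more. From SAP 4.3: one-sample chi-square test, one-sided 0.025. SAP 4.3 gives no sample size, so n = 43 is an assumption, taken from the primary analysis.

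**1. The plan's own figure.** The probability of rejecting at a cut-off r is the sum over x = 9 to 15 of P(X1 = x) × P(X2 ≥ r − x), with X1 binomial on 15 subjects and X2 binomial on 43 − 15 = 28. For r = 27:
- at a rate of 0.50: 0.0499, stated as 0.05;
- at a rate of 0.70: 0.804, stated as 0.801.

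The stated design is reproduced. A search over two-stage designs for 50% versus 70%, with type I error at most 0.05 and power at least 0.80, also returns this one (8/15, then 26/43 as the last failing count) as the design with the smallest expected sample size under the null.

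**2. The SAP 4.3 test at n = 43.** z = (x − 21.5) / √(43/4) = (x − 21.5) / 3.279.
- x = 27: z = 5.5 / 3.279 = 1.677, chi-square 2.814, one-sided p = 0.0467. This does not reach 0.025.
- x = 28: z = 6.5 / 3.279 = 1.982, chi-square 3.930, one-sided p = 0.0237. This does.

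At 28/43 the continuity-corrected p is 0.0336 and the exact binomial p is 0.0330, so under either of those the cut-off is 29/43. At n = 54 the cut-off would be 35. No version of the test that was tried at n = 43 and one-sided 0.025 gives 27.

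**3. What the shift would do to error and power.**

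| Cut-off | Type I error, with 8/15 stop | Power at 70%, with 8/15 stop | Type I error, single stage | Power at 70%, single stage |
|---|---|---|---|---|
| 27/43 | 0.0499 | 0.804 | 0.0631 | 0.883 |
| 28/43 | 0.0279 | 0.750 | 0.0330 | 0.808 |
| 29/43 | 0.0141 | 0.669 | 0.0158 | 0.708 |

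The drop in power to 0.750 appears only if the SAP 4.3 cut-off is combined with the futility stop of SAP 3.2.1. Read as the single-stage test that SAP 4.3 describes, 28/43 has power 0.808, above the stated 0.801, with exact type I error 0.033 rather than 0.025.

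**4. Whether either rule can be applied.** With 5 treated patients there can be at most 5 responses. The first stage needs 9 of 15, and the final rule needs 27 or 28 of 43. Neither is reachable, and the SAP schedules neither.

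**The case for a change.** The best case for a change is that the SAP is the governing statistical record, that it restates the whole design, and that it gives two significance levels for the primary endpoint. A reader who took SAP 4.3 as the definitive statement would get the test, the level and the alternative wrong. The correction would be wording only.

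The inconsistency stands, and so does the point about the malformed alternative. Three supporting arguments do not hold as far as they are usually pressed.

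- *SAP 4.3 governs.* Nothing ranks SAP 4.3 above SAP 3.2.1. Section 3.2.1 is equally SAP text, is the more specific of the two, and agrees with the protocol. A statistician who had to choose would follow it.
- *The stated power is lost.* As shown above, that depends on a hybrid of the two sections. The single-stage reading keeps the power and slightly overruns its nominal level.
- *A success at the boundary would sit beside a 95% interval containing the null.* The exact interval for 27/43 is 46.7% to 77.0%, which does include 50%. But the two-sided 95% interval in Protocol 14.2 is for the wild-type subset of the Full Analysis Set, whereas the 27/43 rule applies to the first 43 evaluable subjects regardless of mutation status. No interval is specified for that decision set, and a descriptive 95% interval beside a one-sided 0.05 rule is not in itself an error.

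**Conclusion.** No change is needed, because a correction would bring no gain. SAP 4.3 conflicts with SAP 3.2.1 and Protocol 14.6, and on 43 subjects the difference is one response (27 versus 28) without continuity correction, or two (27 versus 29) with a correction or an exact test. Its alternative also leaves the range between 50% and 70% unassigned.

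The text cannot affect anything the trial does or reports. The SAP was prepared for a synoptic report after termination with 5 treated patients, excludes all futility and efficacy analyses, and defines no population on which the test could be run. Following the plan exactly as written gives no wrong result. The design on which the trial was sized is stated consistently in the protocol and in SAP 3.2.1, and its error rate and power check out.

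This conclusion rests on the SAP's statements that no efficacy analysis will be performed. Had the trial continued to 43 evaluable subjects, the same conflict would have had to be settled before the primary analysis.
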